## 6.6 Data Summarization and Presentation

All LOXO-292 PK concentrations and PK parameters descriptive statistics will be generated using SAS® Version 9.3 or higher.

The plasma concentrations of LOXO-292 will be listed and summarized by treatment and time point for all subjects in the PK Population. Plasma concentrations of LOXO-

292 will be presented with the same level of precision as received from the bioanalytical laboratory. Summary statistics, including sample size (n), arithmetic mean (Mean), standard deviation (SD), coefficient of variation (CV%), standard error of the mean (SEM), minimum, median, and maximum will be calculated for all nominal concentration time points. Excluded subjects will be included in the concentration listings, but will be excluded from the summary statistics and noted as such in the tables. All BLQ values will be presented as “BLQ” in the concentration listings and footnoted accordingly.

Mean and individual concentration-time profiles will be presented on linear and semi-log scales. Linear mean plots will be presented with and without SD.

Plasma LOXO-292 PK parameters will be listed and summarized by treatment for all subjects in the PK Population. Pharmacokinetic parameters will be reported to 3 significant figures for individual parameters, with the exception of Tmax and  $t_{1/2}$ , which will be presented with 2 decimal places. Summary statistics (n, Mean, SD, CV%, SEM, minimum, median, maximum, geometric mean [Geom Mean] and geometric CV% [Geom CV%]) will be calculated for plasma LOXO-292 PK parameters. Excluded subjects will be listed in the PK parameter tables, but will be excluded from the summary statistics and noted as such in the tables.

The level of precision for each concentration and PK parameter statistic will be presented as follows:

- minimum/maximum in same precision as in bioanalytical data and parameter output,
- mean/median in one more level of precision than minimum/maximum,
- SD/SEM in one more level of precision than mean/median,
- n will be presented as an integer, and
- CV% will be presented to the nearest tenth.

## 6.7 Statistical Analysis of PK Parameters

A comparison of ln-transformed PK parameters (AUC0-t, AUC0-inf, and Cmax) will be made to evaluate the effect of:

- Food on the single-dose administration of LOXO-292 (Treatment B Versus Treatment A);
- The effect of gastric pH change by multiple-dose administrations of omeprazole on the single-dose administration of LOXO-292 under fasted conditions (Treatment C Versus Treatment A);

- The effect of gastric pH change by multiple-dose administrations of omeprazole on the single-dose administration of LOXO-292 under fed conditions (Treatment D Versus Treatment B);
- The effect of food on the single-dose administration of LOXO-292 under gastric pH change by multiple-dose administrations of omeprazole (Treatment D Versus Treatment C)

by performing an analysis of variance (ANOVA) model using PROC MIXED in SAS®.

The ANOVA model will include sequence and treatment as the fixed effects and

## 7. SAFETY

No inferential statistics are to be performed for the safety analysis.

All clinical safety and tolerability data will be listed by subject and assessment time points, including rechecks, unscheduled assessments, and early termination (ET), chronologically.

Continuous variables will be summarized using n, arithmetic mean, SD, minimum, median, and maximum. Frequency counts will be reported for categorical data when appropriate.

The level of precision will be presented as follows: “n” as an integer, minimum/maximum in same precision as in the database, mean/median in one more precision level than minimum/maximum, and SD in one more precision level than mean/median.

Where individual data points are missing because of dropouts or other reasons, the data will be summarized based on reduced denominators.

When change from baseline is calculated, baseline is the last scheduled assessment before dosing of LOXO-292 at each period, including rechecks and unscheduled assessments, whichever is later, unless otherwise specified in the sections below. Rechecks, unscheduled assessments and ET measurements taken after first dosing will not be used in the summarization.

### **7.1 Subject Discontinuation**

Subjects will be summarized by the number of subjects enrolled, completed, and discontinued from the study with discontinuation reasons by treatment sequence and overall. Individual subject’s dosing status for each treatment will be provided along with their study completion status and date. Disposition data will be listed by subject.

### **7.2 Demographics**

Descriptive statistics will be calculated for continuous variables (age, weight, height, and body mass index) by treatment sequence and overall. Weight, height and body mass index are summarized at screening. Age will be derived from the date of birth to the date of first dosing. Frequency counts will be provided for categorical variables (race, ethnicity, and sex). A by-subject listing will also be provided.

### **7.3 Adverse Events**

All adverse events (AEs) occurring during this clinical trial will be coded using the Medical Dictionary for Regulatory Activities (MedDRA®), Version 21.0.

Each AE will be graded, by the clinical site, on the National Institution of Health’s Common Terminology Criteria for Adverse Events (CTCAE, version 5.0) 5-point severity scale (Grades 1, 2, 3, 4 and 5). Not all grades are appropriate for all AEs, therefore some AEs are listed in the CTCAE with fewer than 5 options for grade selection. The following definitions for clinical descriptions of severity grade for each AE are based on the following general guideline [[CTCAE Nov 2017](#)]:

**Table 7.3: Adverse Event Severity Grade Level and Description**

Grade	Description
Grade 1	Mild; asymptomatic or mild symptoms; clinical or diagnostic observations only; intervention not indicated.
Grade 2	Moderate; minimal, local or noninvasive intervention indicated; limiting age-appropriate instrumental ADL*.
Grade 3	Severe or medically significant but not immediately life-threatening; hospitalization or prolongation of hospitalization indicated; disabling; limiting self care ADL**.
Grade 4	Life-threatening consequences; urgent intervention indicated.
Grade 5	Death related to AE.

\* Instrumental ADL refer to preparing meals, shopping for groceries or clothes, using the telephone, managing money, etc.  
\*\* Self care ADL refer to bathing, dressing and undressing, feeding self, using the toilet, taking medications and not bedridden.

Similarly, the causal relationship of the study drugs to the AE will be described as Related or Unrelated to study drugs LOXO-292 and/or omeprazole.

All AEs captured in the database will be listed in by-subject data listings including verbatim term, coded term, treatment group, severity grade, relationship to study drugs, and action; however, only treatment-emergent AEs (TEAEs) will be summarized.

A TEAE is defined as an undesirable event not present prior to medical treatment, or an already present event that worsens either in intensity or frequency following the treatment. Each TEAE will be attributed to a treatment based on investigator judgment as well as its onset date and time. An AE that occurs during the washout period between treatments will be considered treatment-emergent to the last treatment given. If an AE has a change in severity grade, the original AE will be given a resolution date and time, of the time of severity grade increase or decrease, and a new AE record will be initiated with the new severity grade, and the new AE record will use the resolved date/time of the previous record as onset date/time. If an AE decreases in severity grade, the new AE record with less severity will be considered and counted as the same AE event of the previous record with worse severity under

the same treatment group and period in the analysis and summary tables. If the severity of an AE remains the same, the AE will be kept open through to resolution.

If the onset time of an AE is missing and the onset date is the same as the LOXO-292 treatment dosing date, then the AE will be considered treatment-emergent in both the prior and current treatment. If the onset time of an AE is missing and the onset date does not fall on a LOXO-292 dosing date, then the AE will be considered treatment-emergent for the last treatment administered. If the onset date of an AE is missing, then the AE will be considered treatment-emergent and attributed to the first treatment group on the study, unless the onset date is known to have occurred within or between specific treatment periods.

TEAEs will be tabulated by system organ class and preferred term. Summary tables will include the number of subjects reporting the AE and as a percent of the number of subjects dosed by treatment and overall. In addition to the protocol defined Treatments A, B, C, D, an additional treatment OMP Alone will be used to account for the time period of omeprazole administered alone, i.e., multiple daily doses of 40 mg omeprazole (1 x 40 mg capsule) from Day -4 to Day -1 of Period 3. In addition, the number of AEs will be summarized. Tables will also be presented by severity grade and relationship to study drugs. If a subject experienced the same TEAE more than once with different level of severity grade for a given treatment, only the most severe one will be counted. Similarly, if a subject experienced the same TEAE more than once with different level of drug relationship for a given treatment, only the one most closely related to the study drug will be counted.

Should any serious adverse events (SAEs) occur during the study, the SAEs will be displayed in a table and a narrative included in the Clinical Study Report.

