13.2.7.3 Reporting

All AEs that occurred during this clinical study will be recorded. The start of the AE reporting for a subject will be the signing of informed consent for this study. Between the time of informed consent and with the first dose of study drug, only AEs (non-serious and serious) assessed as related to study procedures should be reported. All other events should be reported as medical history. After the first dose of study drug, all AEs (serious and non-serious, related and unrelated) should be reported. Unless a subject withdraws consent for follow-up, all subjects must be followed until the end of the AE reporting period at 7 days after the last study drug administration (omeprazole or LOXO-292, whichever comes last) or when any ongoing drug-related AEs and/or SAEs have resolved or become stable. The PI should use appropriate judgment in ordering additional tests as necessary to monitor the resolution of events. The Sponsor may request that certain AEs be followed longer and/or additional safety tests be performed.

The PI or designee will review each event and assess its relationship to drug treatment (yes [related] or no [unrelated]). Each sign or symptom reported will be graded on the National

Institution of Health's Common Terminology Criteria for Adverse Events (CTCAE) version 5.0 toxicity grading scale.

Grade refers to the severity of the AE. The CTCAE displays Grades 1 through 5 with unique clinical descriptions of severity for each AE based on the following general guideline [[CTCAE Nov 2017](#)]:

Grade 1	Mild; asymptomatic or mild symptoms; clinical or diagnostic observations only; intervention not indicated.
Grade 2	Moderate; minimal, local or noninvasive intervention indicated; limiting age-appropriate instrumental ADL*.
Grade 3	Severe or medically significant but not immediately life threatening; hospitalization or prolongation of hospitalization indicated; disabling; limiting self-care ADL**.
Grade 4	Life-threatening consequences; urgent intervention indicated.
Grade 5	Death related to AE.

A Semi-colon indicates 'or' within the description of the grade.

Note: Activities of Daily Living (ADL)

* Instrumental ADL refer to preparing meals, shopping for groceries or clothes, using the telephone, managing money, etc.

** Self care ADL refer to bathing, dressing and undressing, feeding self, using the toilet, taking medications, and not bedridden.

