### 3. STUDY DESIGN

This is an open label, randomized, 4-treatment, crossover study.

CCI [REDACTED] healthy, adult male and female subjects (women of non-childbearing potential only) were enrolled. Every attempt were made to enroll at least 3 subjects of each sex in the study.

Screening of subjects occurred within 28 days prior to the first dosing.

Subjects were randomized to one of four treatment sequences: ABCD, ABDC, BACD, and BADC. Every attempt was made to include the same number of females in each sequence and the same number of males in each sequence.

On Day 1 of Periods 1 and 2, a single oral dose of LOXO-292 was administered under fasted or fed conditions, according to the randomization schedule, followed by PK sampling for 168 hours.

In Periods 3 and 4, multiple oral doses of omeprazole were administered once daily from Day -4 of Period 3 until Day 7 of Period 4, inclusive (for a total of 18 consecutive days) with a single oral dose of LOXO-292 coadministered on Day 1 of each period under fasted or fed conditions, according to the randomization schedule. Pharmacokinetic sampling for LOXO-292 was taken for 168 hours following LOXO-292 dosing on Day 1 in each period.

There was a washout period of 7 days between LOXO-292 dose in Period 1 and LOXO-292 dose in Period 2 and between the LOXO-292 dose in Period 2 and the first dose of omeprazole in Period 3. There was no washout between Periods 3 and 4 omeprazole doses although the LOXO-292 doses will be separated by a 7-day washout.

Safety was monitored throughout the study by repeated clinical and laboratory evaluations.

Subjects were permitted to be replaced at the discretion of the Sponsor, but no subjects were replaced on this study.

Subjects were housed throughout the study beginning on Day -1 of Period 1, at the time indicated by the CRU, until after completion of the 168-hour blood draw and/or study procedures in Period 4. At all times, a subject may have been required to remain at the CRU for longer at the discretion of the Principal Investigator (PI) or designee.

The CRU made every attempt to contact all subjects who received at least 1 dose of study drug (including subjects who terminated the study early) using their standard procedures (i.e., phone call or other method of contact) approximately 7 days after the

last study drug administration (LOXO-292 or omeprazole, whichever came last) to determine if any AE had occurred since the last study visit.

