			Minimum	XX.X	XX.X	XX.X	XX.X	XX.X	XX.X	XX.X	XX.X
			Median	XX.XX	XX.XX	XX.XX	XX.XX	XX.XX	XX.XX	XX.XX	XX.XX
			Maximum	XX.X	XX.X	XX.X	XX.X	XX.X	XX.X	XX.X	XX.X

<Programmer note: Similar for remaining laboratory tests. Sort alphabetically by lab test name.>

Note: # Lowest of the lower ranges and highest of the higher ranges are used. Refer to Appendix 16.1.10.1 for the breakdown.

\$ Day 7 for Period 1, 2, 3 and Day 8 for Period 4

Baseline is Day -1 of Period 1 and Day 7 of previous period for Period 2, 3, 4 and is the last non-missing predose measurement prior to dosing of LOXO-292, including rechecks and unscheduled assessments. Day 7 measurement of Period 1, 2, 3 was used twice as postdose value of Period 1, 2, 3 and baseline value of Period 2, 3, 4.

Treatment A: <description>

Treatment B: <description>

Treatment C: <description>

Treatment D: <description>

Prior to Treatment C or D at Period 3, subjects were administered with multiple daily doses of 40 mg omeprazole (1 x 40 mg capsule) from Day -4 to Day -1 of Period 3.

Program: /CAXXXX/sas\_prg/stsas/tab\_PROGRAMNAME.sas DDMMMYYYY HH:MM

Tables 14.3.5.2, 14.3.5.4, and 14.3.5.6 will have the following format.

Page 1 of X

Table 14.3.5.2 Clinical Laboratory Shift from Baseline - Serum Chemistry (Safety Population)

Laboratory Test (units)	Treatment	Time Point	Baseline L			Baseline N			Baseline H		
			Postdose			Postdose			Postdose		
			L	N	H	L	N	H	L	N	H
Testname(unit)	A	Day 4	X	XX	X	X	XX	X	X	XX	X
		Day 7	X	XX	X	X	XX	X	X	XX	X
	B	Day 4	X	XX	X	X	XX	X	X	XX	X
		Day 7	X	XX	X	X	XX	X	X	XX	X
	C	Day 4	X	XX	X	X	XX	X	X	XX	X
		Day 7/8\$	X	XX	X	X	XX	X	X	XX	X
	D	Day 4	X	XX	X	X	XX	X	X	XX	X
		Day 7/8\$	X	XX	X	X	XX	X	X	XX	X

< > < >

<Programmer note: Similar for remaining laboratory tests. Use N = Within Normal Range, O = Outside Normal Range for urinalysis shift table.>

Note: N = Within Normal Range, L = Below Normal Range, H= Above Normal Range.

\$ Day 7 for Period 3 and Day 8 for Period 4

Baseline is Day -1 of Period 1 and Day 7 of previous period for Period 2, 3, 4 and is the last non-missing predose measurement prior to dosing of LOXO-292, including rechecks and unscheduled assessments. Day 7 measurement of Period 1, 2, 3 was used twice as postdose value of Period 1, 2, 3 and baseline value of Period 2, 3, 4.

Treatment A: <description>

Treatment B: <description>

Treatment C: <description>

Treatment D: <description>

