Prior to Treatment C or D at Period 3, subjects were administered with multiple daily doses of 40 mg omeprazole (1 x 40 mg capsule) from Day -4 to Day -1 of Period 3.

Program: /CAXXXXX/sas\_prg/stsas/tab\_programname.sas DDMMYYYY HH:MM

Table 14.3.5.7 Vital Sign Summary and Change from Baseline (Safety Population)

Vital Sign Parameter (unit)	Time Point	Statistic	Treatment				Change From Baseline			
			A	B	C	D	A	B	C	D
Parameter1 (unit)	Day -1/1\$	n	XX	XX	XX	XX				
		Mean	XX.XX	XX.XX	XX.XX	XX.XX				
		SD	X.XXX	X.XXX	X.XXX	X.XXX				
		Minimum	XX.X	XX.X	XX.X	XX.X				
		Median	XX.XX	XX.XX	XX.XX	XX.XX				
		Maximum	XX.X	XX.X	XX.X	XX.X				
	Postdose Hour 2	n	XX	XX	XX	XX	XX	XX	XX	XX
		Mean	XX.XX	XX.XX	XX.XX	XX.XX	XX.XX	XX.XX	XX.XX	XX.XX
		SD	X.XXX	X.XXX	X.XXX	X.XXX	X.XXX	X.XXX	X.XXX	X.XXX
		Minimum	XX.X	XX.X	XX.X	XX.X	XX.X	XX.X	XX.X	XX.X
		Median	XX.XX	XX.XX	XX.XX	XX.XX	XX.XX	XX.XX	XX.XX	XX.XX
		Maximum	XX.X	XX.X	XX.X	XX.X	XX.X	XX.X	XX.X	XX.X
	Postdose Hour 72	n	XX	XX	XX	XX	XX	XX	XX	XX
		Mean	XX.XX	XX.XX	XX.XX	XX.XX	XX.XX	XX.XX	XX.XX	XX.XX
		SD	X.XXX	X.XXX	X.XXX	X.XXX	X.XXX	X.XXX	X.XXX	X.XXX
		Minimum	XX.X	XX.X	XX.X	XX.X	XX.X	XX.X	XX.X	XX.X
		Median	XX.XX	XX.XX	XX.XX	XX.XX	XX.XX	XX.XX	XX.XX	XX.XX
		Maximum	XX.X	XX.X	XX.X	XX.X	XX.X	XX.X	XX.X	XX.X

<Programmer note: Similar for remaining vital sign parameters. Treatment D has an additional time point: Postdose Hour 168.>

Note: \$ Day -1 for Period 1 and Day 1 for Period 2, 3, 4

Baseline is Day -1 of Period 1 and Day 1 predose of Period 2, 3, 4 and is the last non-missing predose measurement prior to dosing of LOXO-292, including rechecks and unscheduled assessments.

Treatment A: <description>

Treatment B: <description>

Treatment C: <description>

Treatment D: <description>

Prior to Treatment C or D at Period 3, subjects were administered with multiple daily doses of 40 mg omeprazole (1 x 40 mg capsule) from Day -4 to Day -1 of Period 3.

Program: /CAXXXX/sas\_prg/stsas/tab\_PROGRAMNAME.sas DDMMMYYYY HH:MM

Table 14.3.5.8 12-Lead Electrocardiogram Summary and Change from Baseline (Safety Population)

ECG Parameter (unit)	Time Point	Statistic	Treatment				Change From Baseline			
			A	B	C	D	A	B	C	D
Parameter1 (unit)	Day -1/1\$	n	XX	XX	XX	XX				
		Mean	XX.XX	XX.XX	XX.XX	XX.XX				
		SD	X.XXX	X.XXX	X.XXX	X.XXX				
		Minimum	XX.X	XX.X	XX.X	XX.X				
		Median	XX.XX	XX.XX	XX.XX	XX.XX				
		Maximum	XX.X	XX.X	XX.X	XX.X				
	Postdose Hour 2	n	XX	XX	XX	XX	XX	XX	XX	XX
		Mean	XX.XX	XX.XX	XX.XX	XX.XX	XX.XX	XX.XX	XX.XX	XX.XX

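### SAP Tables 14.3.5.7 and 14.3.5.8 give the 168-hour vital sign and ECG row to Treatment D only, although half of the sequences end in Treatment C

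*SAP*

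**What the plan says.** SAP Tables 7.5 and 7.6 list the vital sign and ECG time points by period, without naming a treatment. The last row of each is Period 4, Day 8, Hour 168, done at the end of Period 4 or before early termination. SAP 7.5 and 7.6 then call for descriptive statistics and change from baseline by treatment and time point. Protocol 14.3.2 also asks for safety data by treatment and time of collection.

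The shells for Tables 14.3.5.7 and 14.3.5.8 have columns A, B, C and D and rows for baseline, Hour 2 and Hour 72. The programmer note under each adds: "Treatment D has an additional time point: Postdose Hour 168". Neither shell says that C has this row too.

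The laboratory shift shell (Table 14.3.5.2) treats the same design feature differently. It gives a Day 7/8 row to both C and D, with the footnote "Day 7 for Period 3 and Day 8 for Period 4".

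The four sequences are ABCD, ABDC, BACD and BADC (protocol 10.1 and 12.3; SAP Section 3).

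On adverse events, which also have to be placed after Period 4, SAP 7.3 begins: "A TEAE is defined as an undesirable event not present prior to medical treatment". It adds worsening of an existing event and gives no end day.

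**The concern.** The note treats D as the treatment given last. That is true of ABCD and BACD but not of ABDC and BADC, where the last treatment is C. The 168-hour assessment belongs to a period, and the shell ties it to a treatment.

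At stake are the only scheduled vital signs and ECGs after Hour 72 of the final period. For subjects who end on C, these values and their changes from baseline would either disappear from the summary or appear under a treatment that those subjects received a period earlier. In the first case the D column would show a smaller n at Hour 168 than at Hours 2 and 72, with no explanation. In the second it would mix two treatments under one label.

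**Working it through.** **Calendar.** The inputs are the 7-day LOXO-292 intervals and the start of omeprazole on Day -4 of Period 3 (protocol 10.1), which is the same day as Day 8 of Period 2 (protocol flow chart footnotes). In study days: Period 1 Day 1 = 1, Period 2 Day 1 = 8, Period 3 Day -4 = 15, Period 3 Day 1 = 19, Period 4 Day 1 = 26, Period 4 Day 7 = 32. Check against the plan's own figure: omeprazole days = 32 - 15 + 1 = 18, as stated. The 168-hour point in Period 4 falls on 26 + 168/24 = 33, which is Period 4 Day 8.

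**Treatment at the 168-hour assessment.**

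| Sequence | Period 3 | Period 4 | Treatment at Hour 168 | Row in the shell? |
|---|---|---|---|---|
| ABCD | C | D | D | yes |
| BACD | C | D | D | yes |
| ABDC | D | C | C | no |
| BADC | D | C | C | no |

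So 2 of 4 sequences have no correct place for the measurement.

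**Can D have an Hour 168 value in ABDC and BADC?** No. Tables 7.5 and 7.6 schedule nothing at Hour 168 in Periods 1 to 3. The assessment nearest to that time after the Period 3 dose is the Period 4 predose one, which the SAP uses as the Period 4 baseline. The D-only note cannot be rescued by reading it as Day 8 of Period 3.

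**Share of subjects.** With n subjects completing in each sequence, 2n of 4n = 50% have the assessment under C. Equal allocation is an assumption, but a natural one: the protocol aims for the same number of each sex in each sequence. The sample size is redacted. If it were 12 to 24 (assumed), 6 to 12 subjects would be affected.

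**What the table would show.**

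- Row printed for D only and filled by actual treatment: D has 2n values, and the 2n values under C are absent.
- Row filled from all Period 4 data and labelled D: D shows 4n values, of which 2n were taken under C.
- Row for C and D, filled by Period 4 treatment: C has 2n and D has 2n, which matches the schedule.

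The laboratory shift shell already follows the third pattern.

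**The case against.** The strongest reply is that shells are only a framework. SAP Section 10 says that they may change and may not reflect every aspect of the study. A programmer working by period and treatment would probably see the problem, and the by-subject listings (Appendices 16.2.8.2 and 16.2.8.3) show each value with its period and treatment. SAP Section 7 plans no inference on safety. All of this stands as a limit on the size of the point. It does not remove it, because a general caveat does not correct a specific instruction that appears twice and conflicts with the SAP's own schedule.

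A reader might infer more: that adverse events after Period 4 are misplaced in the same way, or that the TEAE percentages for C and D are inflated by a longer window. The starting observation is correct. SAP 7.3 gives no TEAE end day, and its washout rule, "An AE that occurs during the washout period between treatments will be considered treatment-emergent to the last treatment given", does not name the time after release on study Day 33. Counting to the end of AE reporting (32 + 7 = Day 39), Period 4 covers 39 - 26 = 13 days. A, B and Period 3 cover 7 each, and omeprazole alone covers 4.

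The documents do not support calling this an error:

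- Protocol 13.2.7.3 bounds routine collection: "all subjects must be followed until the end of the AE reporting period at 7 days after the last study drug administration".
- SAP 7.3 attributes every TEAE by investigator judgment together with onset date and time. After Period 4 no later treatment exists, so this leads to the Period 4 treatment. The rule for missing onset times follows the same convention: "the onset date does not fall on a LOXO-292 dosing date, then the AE will be considered treatment-emergent for the last treatment administered".
- The footnotes of Table 12-1 already show the 4-day omeprazole-alone span and the Day 1 to Day 7 omeprazole span. Only the days after release are unstated.
- Vital sign and ECG shells are no evidence of how adverse events will be assigned.

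The possible effect is also small. Assume 12 to 24 subjects, a 7-day AE risk of 20% and no drug effect. If no post-release event is detected, the C or D column gains nothing. With constant hazard and full detection, Period 4 would show 1 - 0.8^(13/7) = 33.9%. Averaged with 20% for Period 3, the column would show 26.96%, a gain of 0.0696 x 12 = 0.8 to 0.0696 x 24 = 1.7 subjects. That is an upper bound, since a single open-ended follow-up contact covers those days.

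**Conclusion.** The programmer notes of Tables 14.3.5.7 and 14.3.5.8 are wrong as written. They contradict SAP Tables 7.5 and 7.6 combined with the randomisation sequences, and they differ from the SAP's own laboratory shift shell. The conflict needs no assumption: 2 of 4 sequences are affected. That this means half of the completing subjects rests on balanced sequences and similar completion across them.

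The consequence is confined to one time point in two descriptive safety tables. No PK parameter, comparison or confidence interval depends on it. The missing TEAE end day and post-release sentence, the unstated AE windows, and the undefined reference dose for time from last dose in Appendix 16.2.7.1 are places where a clarification would be welcome. They are not errors.

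**What to change.** Change both programmer notes so that the Hour 168 row, with its change from baseline, appears for C and D. Fill each column only from subjects who received that treatment in Period 4, and add a footnote such as: Hour 168 measured in Period 4 only. Keep early-termination values out, as SAP 7.5 and 7.6 already require. If the tables have been programmed, check that n at Hour 168 under C equals the completers of ABDC and BADC with a value, and under D those of ABCD and BACD.

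The cost is two edited notes and two footnotes, with no new data or analysis. Each Hour 168 cell will rest on about half of the subjects, which the footnote explains.

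Optional, if SAP 7.3 is being edited anyway: refer to the protocol's AE reporting period, say that events starting after Period 4 release go to the last treatment received, note the days covered by each TEAE column, and say which drug time from last dose refers to. An end day should state how a later SAE reported under protocol 13.2.7.4 is shown, since a strict cut-off would remove it from the TEAE counts.

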12.4 Blinding

This is an open-label study.

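### SAP 7.3 uses investigator judgment alongside onset time to choose each adverse event's treatment column, with no rule for disagreement, although a recorded onset already identifies the column

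*SAP*

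**What the plan says.** The general attribution rule, in the text after Table 7.3 of SAP 7.3, covers every treatment-emergent adverse event (TEAE): "Each TEAE will be attributed to a treatment based on investigator judgment as well as its onset date and time". The sentence after it uses timing only: "An AE that occurs during the washout period between treatments will be considered treatment-emergent to the last treatment given". The same section adds a fifth column for the adverse event tables, under which "an additional treatment OMP Alone will be used to account for the time period of omeprazole administered alone"; SAP Section 5 and SAP 7.3 both date it from Day -4 to Day -1 of Period 3.

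Causality is recorded separately: "the causal relationship of the study drugs to the AE will be described as Related or Unrelated to study drugs LOXO-292 and/or omeprazole". Tables 14.3.1.3 and 14.3.1.4 have one set of relationship columns for each drug.

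Protocol 12.4 says: "This is an open-label study". Protocol 13.2.7.3 gives the investigator the related/unrelated call. Protocol 14.3.2 has TEAEs summarized by treatment and does not mention judgment as a way of choosing the treatment. SAP Section 8 reports no departure from the protocol's analyses.

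**The concern.** The treatment column is what the by-treatment adverse event tables compare, and the secondary objective concerns tolerability with and without food, alone or with omeprazole. If the column depends partly on the opinion of someone who knows the treatment, a prior belief about food, LOXO-292 or omeprazole can enter the counts. The sentence names two criteria, gives no order of precedence, and does not ask for a disagreement to be recorded. The investigator's opinion also has its own place in the relationship fields, so using it again to choose the column adds subjectivity without adding information.

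**Working it through.** There is no planned figure to reproduce: the sample size is redacted and SAP Section 7 plans no safety inference. The check is whether timing alone settles the column, where it does not, and how far one event could move a table.

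**1. Does onset identify one column?** The study days come from Protocol Section 6 (Tables 1 and 2 with footnotes), the omeprazole-alone dates from SAP Section 5, and the end of adverse event reporting (7 days after the last study drug) from Protocol 13.2.7.3.

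| Window | Study days | Length (days) | Column |
|---|---|---|---|
| Period 1 | 1–7 | 7 | A or B |
| Period 2 | 8–14 | 7 | B or A |
| Period 3, Day -4 to Day -1 | 15–18 | 4 | OMP Alone |
| Period 3 from Day 1 | 19–25 | 7 | C or D |
| Period 4 and follow-up | 26–39 | 14 | D or C |

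- Calendar check: omeprazole runs 4 + 7 + 7 = 18 days, and study days 15 to 32 give 32 − 15 + 1 = 18. This matches the 18 days in Protocol 10.1.
- The last window ends on day 32 + 7 = 39.
- The lengths sum to 7 + 7 + 4 + 7 + 14 = 39, so days 1 to 39 are covered with no gap and no overlap.
- On the changeover days (8, 15, 19 and 26) the clock time decides, and Protocol 12.1 requires the exact dosing time to be recorded.

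A complete onset date and time therefore points to one column. For such an event, judgment either agrees with timing or contradicts it.

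**2. What do the rules for incomplete onset do?** All are in SAP 7.3.

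- Time missing, date is a LOXO-292 dosing date: "then the AE will be considered treatment-emergent in both the prior and current treatment".
- Time missing, any other date: "then the AE will be considered treatment-emergent for the last treatment administered".
- Date missing: "attributed to the first treatment group on the study, unless the onset date is known to have occurred within or between specific treatment periods".

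These are defaults based on timing, but two gaps remain.

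- *First omeprazole dose (Period 3 Day -4, study day 15).* This is not a LOXO-292 dosing date, so the second rule applies. With the time missing, the last treatment administered could be the Period 2 treatment or omeprazole.
- *Worsening in frequency.* SAP 7.3 counts a pre-existing event as treatment-emergent if its intensity or frequency worsens. Only a change of severity grade opens a new record with a new onset; otherwise the record stays open until resolution. An event that starts under A and becomes more frequent under C has no recorded onset under C.

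**3. How much can one event move a table?** Assume N subjects dosed in each column, with N from 12 to 24. Tables 12-1 and 14.3.1.1 give percentages of subjects dosed, and Table 12-1 counts a subject once within a category. A column changes only if the moved event was the subject's only one of that category in the column it leaves, or if the subject had none of that category in the column it enters.

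- Change in one column, at most 1/N: 1/24 = 4.2 and 1/12 = 8.3 percentage points.
- Change in a difference when only one of the two compared columns is affected, at most 1/N: 4.2 to 8.3 points.
- Change in a difference when both affected columns are the ones compared, at most 2/N: 2/24 = 8.3 and 2/12 = 16.7 points.

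The denominators do not change.

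**The case against.** The strongest reply is that the sentence joins judgment to onset and does not put judgment in its place. The more specific sentences that follow work by timing: washout events go to the last treatment given, and missing times have fixed defaults. This stands. A reader might infer that the investigator is free to move events between the fed, fasted and omeprazole columns, but the text does not say so.

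A reader might also suppose that nausea on Day -2 of Period 3 could be placed under A or B because LOXO-292 is suspected. Nothing in the SAP sends it there: the OMP Alone column was added for those days, and the suspicion belongs in the LOXO-292 relationship field.

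Nor do the documents support a claim that the attribution could not be checked. Appendix 16.2.7.1 lists treatment, time from last dose, and onset date and time for each event, and Appendix 16.2.5.4.2 lists dosing times, so a mismatch can be found. The adverse event tables are also not the whole safety comparison, because laboratory tests, vital signs and ECGs are tabulated by treatment in Tables 14.3.5.1 to 14.3.5.8.

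Finally, judgment has a legitimate use where an existing event becomes more frequent without a change of grade. This also stands, and simply deleting the criterion would lose it. None of these replies supplies an order of precedence or shows that judgment is needed when onset is fully recorded.

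**Conclusion.** The point holds as a rule that should be tightened. SAP 7.3 names a subjective criterion for every TEAE in an open-label trial, gives no precedence over onset, and does not need it where onset date and time are recorded. Its reach is limited to the descriptive by-treatment adverse event tables. The pharmacokinetic comparisons are untouched and safety has no inference to distort.

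The sizes of 4.2 to 8.3 points for a column, and up to 8.3 to 16.7 points for a difference, are upper bounds. They rest on an assumed 12 to 24 subjects and on the moved event being the subject's only one of its kind. The larger range applies only when both affected columns are being compared. The protocol leaves detailed methods to the SAP, so its silence on judgment is not a contradiction. It does mean that the protocol gives no independent support for this criterion.

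**What to change.** In SAP 7.3:

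1. Strike investigator judgment from the attribution sentence. Assign each TEAE to the last treatment started (A, B, OMP Alone, C or D) before its recorded onset date and time.
2. Keep investigator judgment for the Relationship to LOXO-292 and Relationship to Omeprazole fields, and for deciding whether a pre-existing event worsened in frequency. In that case open a new record with the date of worsening as its onset, so that the timing rule can be applied.
3. Extend the missing-onset-time rule to the first omeprazole dosing date (Period 3 Day -4), for example by counting the event under both the Period 2 treatment and OMP Alone, as is already done on LOXO-292 dosing dates.

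The cost is a few lines of SAP text and one extra record for each event that worsens in frequency only. Programming becomes simpler, because the column follows from dates and times already listed, and the investigator's view of causality is kept.
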